#### **Data collection, management, and storage during COVID-19:**

Considering COVID-19, the transcription of video and audio recordings will be saved in the secured server network of department HOBI or through the password-protected Dropbox cloud. The transcription of voice recordings will be conducted by the research staff and the PI in a secure remote area or by a transcription company.

- **Quality assurance plan (checks for errors):** For all data collections from the proposed project, quality assurance procedures will include a data collection protocol delineating a report on how the data has been collected by each participant, and any potential deviation from the protocol. There will be a two-stage editing procedure for error-checking in data collection, consisting of the initial completion of the Data Collection Form (Appendix 7) by one staff, and a review of the form by another staff who will record any significant deviations from the protocol. Then, survey data is manually revised by the PI to report the presence of any identifying information. Quality assurance procedures will also include regular meetings (approximately monthly) between the study statistician, the PI, and the study staff to review problems and solutions, and discuss concerns in data quality. During data collection, reports will be issued weekly. Preliminary review will be initiated shortly after data collection begins to allow monitoring of data quality.
- **Procedures for preventing and addressing breaches of confidentiality:** Once the survey data is collected, they will be de-identified by replacing names with codes. We will be identifying subjects only by numbers in all data files. Identification numbers will only be connected to individual participant names in a separate file that will be accessible only by the PI. This file will be stored in an encrypted and password protected hard drive, physically locked at the Department of Health Outcomes and Biomedical Informatics at the University of Florida. All study data files will be server-maintained with limited access by using passwords and logins restricted to study staff. All information will be reported in aggregate form, and individual participants will not be identified in any public reports or documents.

All survey, consent documents, and video/audio files will be stored securely in an encrypted and password protected hard drive, physically locked in the department HOBI.

There are two main situations during which confidentiality may be breached because of mandatory reporting requirements: participants' report of child abuse/neglect and suicide risk. The PI or research staff will address child abuse/neglect by reporting it through the Florida Abuse [contact]-ABUSE). This Hotline will provide all reports to the Florida Department of Children and Families. The PI or research staff

will address suicidal ideation by asking the participant to immediately call the National Suicide Prevention Lifeline [contact]), where immediate action can be taken. The PI will also report such an incident to the Florida Department of Children and Families. Child abuse/neglect, suicide risk, and any other adverse event will be reported to the national institute on drug abuse (NIDA; funding agency) and the University of Florida. The parental permission and assent form will mention that such reports may occur.

During the interviews and focus group discussions, we will ask participants to refrain from mentioning anyone's name or any other identifying information. Also in all program sessions, adolescents' conversations will be audio recorded. However, in case a participant mentions identifying information, research staff will erase the segment that mentions identifying information.

#### **Procedures for preventing and addressing breaches of confidentiality during COVID-19 quarantine:**

Considering current COVID-19 quarantine, voice recordings will be taken via Zoom. The transcription of audio recordings will be saved in the secured server network of department HOBI. The transcription of voice recordings will be conducted by the research staff and the PI in a secure remote area or by a transcription company.

Based on IRB's full committee decision following reportable events, Appendix 18 presented the list of the type of data to keep and the type of data to permanently delete from the study.

#### **9. Possible Discomforts and Risks:**

- **Possible discomforts and risks:** No health-related potential risks are expected as a result of the project. The only potential risk concerns confidentiality, because contact information (names and mailing addresses) will be collected from the participants during Study 1 and Study 2. Also, during the focus group sessions (Study 1), interviews (Study 2) and program sessions (Study 2), adolescents may mention someone else's name or their own.
- Also in this study, a participant may mention a concern with the content of the ASPIRE website, the activities, or the content of the survey items.
- **Procedures to protect against or minimize potential discomforts and risks:** While names will be collected, the PI will ensure that the dataset is de-identified immediately after data collection. No identifying information will be collected other than names. However, code numbers will be used to replace names. Also, survey material will be kept anonymous. Participants' names will be kept in locked cabinets and in a password-protected shared drive at the Department of Health Outcomes and Biomedical Informatics at the University of Florida. The links between codes and names will be discarded immediately after survey documents have been linked to each other, and no longer than 1 year after the study has ended. Other than for the assignment to subgroups in the network group, we will not directly be making effort to identify responses, and we will use the links only for matching surveys across times.

In this study, participants will be asked about certain behaviors that they may not want to share with their parents or legal guardians (tobacco use). Their answers will be kept confidential and their parents or legal guardians will not receive their answers.

In case a participant reports a concern regarding the content of the intervention, such participant is offered the opportunity to discontinue with the study. In such a case, any information obtained from this participant will be destroyed. However, a concern with the intervention is deemed unlikely, considering that it is designed specifically to adolescents, with adolescents.

- **Report of adverse events:** The PI and study staff will keep record of any adverse event that may occur, including a brief explanation of the event, when it occurred, the date of the event, description of what occurred, actions taken by research staff, planned follow up (if any), the intervention group/study arm of the

affected participant, whether the event appears to be related to the intervention, and whether the participant will continue in the study.

- The PI may withdraw a participant from the study if their safety may be compromised, when the study is being closed by the PI, the University of Florida, or NIH, or if the participant is non-compliant with required study procedures.

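### Section 9 orders automatic destruction of all data from anyone who discontinues over intervention content: an irreversible exclusion after randomisation, probably small in effect and cheap to correct

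*Combined protocol and SAP*

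**What the plan says.** The rule is in Section 9 (Possible Discomforts and Risks), under the procedures for minimising risk. The trigger is: "In case a participant reports a concern regarding the content of the intervention, such participant is offered the opportunity to discontinue with the study". The consequence follows at once: "In such a case, any information obtained from this participant will be destroyed". The natural reading is that destruction applies when the offer to discontinue is taken up. The protocol expects this to be rare, since "a concern with the intervention is deemed unlikely", but gives no rate. Slightly earlier, the same section says that "a participant may mention a concern with the content of the ASPIRE website, the activities, or the content of the survey items".

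The next part of Section 9, on adverse events, says: "The PI and study staff will keep record of any adverse event that may occur". The record must include the study arm, and also "whether the event appears to be related to the intervention, and whether the participant will continue in the study". Section 8 (procedures on breaches of confidentiality) further requires adverse events to be reported to the funding agency and the university.

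Section 7 (Quantitative data analysis for Study 2) specifies a linear mixed model with 2 conditions and 4 times. It gives no analysis set, no intention-to-treat statement and no rule for missing data.

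**The concern.** Honouring a request for deletion is ordinary practice. Here no request is needed: leaving over content is enough to lose every record, baseline included. The reason for leaving is the participant's reaction to what the club was randomised to receive, so the exclusion is related to treatment by construction.

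Three things are at stake. The comparison is made on a subset defined after randomisation, and nobody can later describe who was taken out of it. The network data lose that respondent's contribution. And staff meet two instructions in the same section, one to keep an event record and one to destroy what was obtained, with nothing to say which prevails.

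**Working it through.** **1. Timing.** Section 7 places baseline and randomisation of clubs on Day 1. Section 8 places randomisation two days after baseline. The first session comes three to five days after orientation. On either account, concerns raised in or after the sessions come after allocation, so the rule acts on randomised participants.

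**2. Exposure by arm.** Section 9 names three possible sources of concern.
- ASPIRE website: both arms.
- Survey items: both arms. The destruction rule itself mentions only intervention content.
- Activities: GSA-ASPIRE-Network only until after Assessment 4, when the ASPIRE arm receives the GSA and network components (Section 7, Study Design).

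Peer grouping is likewise confined to one arm before Assessment 4. The rule names no arm. Differential loss is therefore possible, not established.

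**3. What the analysis can recover.** An ordinary dropout still contributes earlier measurements to a mixed model, and a sensitivity analysis can vary what is assumed about the rest. A participant whose records are destroyed contributes nothing, not even a baseline value on which to condition.

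**4. Network data.** In Section 7 (Social network survey), tie strength is friendship strength multiplied by positive influence, both reported by the respondent. Destroying one respondent's survey removes all of that person's nominations and ratings. Grouping uses the time 1 network, so groups already formed are not undone; the tie data are lost for analysis.

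**5. Safety wording side by side.** Section 9 destroys everything obtained from the participant, without exception. Section 9 (adverse events) requires a record that includes arm, relatedness and continuation. Section 8 requires reporting outside the study team. Taken literally, the first instruction covers records that the other two require.

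**6. The plan's own figures.** Inputs from Section 7 (Sample Size Considerations): 300 participants, 40% retention, 50 non-eligible. 300 / 0.40 = 750, and 750 + 50 = 800, the stated recruitment target. The table of participant numbers agrees: 300 + 450 + 50 = 800. The plan thus allows 450 of 750 (60%) to discontinue, without a split by arm or reason.

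**7. Possible size (illustration).** The planned difference in intention is 1.3 − 0.17 = 1.13 with SD 0.5, which is 1.13 / 0.5 = 2.26 SD. Let f be the share removed from one arm only, and D the gap in SD units between those removed and those retained. The shift in the raw arm mean is f × D × 0.5. Both f and D are assumptions; the documents give neither.

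| f | D | Shift | In SD | Share of 1.13 |
|---|---|---|---|---|
| 1% | 0.25 | 0.00125 | 0.0025 | 0.1% |
| 2% | 0.5 | 0.005 | 0.01 | 0.4% |
| 5% | 0.5 | 0.0125 | 0.025 | 1.1% |
| 10% | 1.0 | 0.05 | 0.10 | 4.4% |
| 20% | 1.0 | 0.10 | 0.20 | 8.8% |

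The sign depends on whether those removed have higher or lower intention, and on which arm loses them.

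**8. Power.** Inputs from Section 7: 2 clubs per arm, 25 per club, ICC 0.3.
- Design effect: 1 + 24 × 0.3 = 8.2. Variance of the difference: 0.25 × (8.2/50 + 8.2/50) = 0.0820. Ratio: 1.13 / √0.0820 = 3.946. Normal-approximation power: 97.6%.
- With 20% removed from one arm, that arm has 20 per club and design effect 1 + 19 × 0.3 = 6.7. Variance: 0.25 × (8.2/50 + 6.7/40) = 0.0829. Ratio: 3.925. Power: 97.5%.

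These levels do not match the plan's 80%, which is a separate matter. Only the change is used here, and it is negligible.

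**The case against.** The strongest case against is that this is a minor clarification. The protocol expects such concerns to be rare; at 2% removed and 0.5 SD, the shift is about 0.4% of the planned difference; and the 450 discontinuations already allowed for, with no missing-data rule, are a far larger threat. On size, this stands. It does not answer the point that the rule, when used, works as an automatic exclusion related to treatment and leaves nothing to examine.

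A second objection is that information obtained from the participant can mean surveys and interviews, as distinct from an event record written by staff, and that a content concern need not be an adverse event. That reading is reasonable, and reports already sent to the funding agency or university would survive. But the text does not draw the distinction, so the passages need reconciling.

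Third, Section 8 refers to Appendix 18, a list of data to keep and to delete that follows an IRB decision after reportable events. The appendix is not in the text, and the consent pages are unavailable. Whether deletion was promised to families cannot be checked. This limits how the fix can be worded but does not remove the need for it.

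A reader might also see a second exit related to arm in the investigator's power to withdraw a participant "if the participant is non-compliant with required study procedures". The documents do not support that. Both arms have five 70-minute sessions over 5 weeks and the same surveys through Assessment 4; the off-session tasks are offered, not required; and over the whole study the ASPIRE arm has the larger schedule. Nor does the text say that the data of those withdrawn are destroyed.

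**Conclusion.** The point holds as a defect of design wording with a probably small numerical effect. Section 9 prescribes an automatic, irreversible exclusion after randomisation, tied to reaction to treatment, that neither the mixed model nor a sensitivity analysis can address. It also removes network nominations and, read literally, conflicts with the recording and reporting of adverse events in Sections 8 and 9.

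Three stronger conclusions might be inferred, and the documents support none of them. That participants are removed selectively by arm: the rule covers both arms, and ASPIRE content is common to both. That safety information is erased: separate duties require events to be recorded and reported; what is shown is a conflict of wording. That the bias favours the intervention: this would need objectors to have higher intention and to sit mainly in GSA-ASPIRE-Network, and neither is documented.

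On the assumed ranges (1% to 20% removed from one arm only, gap 0.25 to 1.0 SD), the arm mean shifts by 0.1% to 8.8% of the planned 1.13, in either direction. Given the plan's own expectation, the lower end is the more likely. The calculation applies the planning SD of 0.5 to all participants. The reason to act is that destroyed data cannot be restored afterwards.

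**What to change.** - Replace the destruction sentence in Section 9 with a rule that data collected up to discontinuation are kept and analysed under the randomised club, unless the participant or parent asks for deletion.
- Exempt adverse-event records from any deletion explicitly, so that the two parts of Section 9 and the reporting duty in Section 8 agree.
- Log the number and arm of any deletions, and report them with the results.

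The right to have data deleted is preserved; only automatic destruction ends. The cost is a change to protocol and consent wording with IRB approval. The consent form must explain that data are retained, and the new wording must be consistent with the list in Appendix 18. The change has to be in place before the rule is next applied.

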## **10. Possible Benefits:**

- By taking part in this study, participants may learn more about general health information, ways to stay healthy, and how to maintain a healthy lifestyle. Future adolescents may benefit from what is learned. There is no additional direct benefit from participating in this study.
- Results from this research study will benefit future populations by allowing us to ensure that we disseminate to future adolescents a well-tested and validated program for tobacco prevention and cessation.
- As researchers, we may benefit professionally if the results of the study are presented at meetings or in scientific journals.

## **11. Compensation:**

- **Participant compensation during Study 1:** Each study participant will receive \$10 in cash or gift card for completing Study 1.
- **Parent compensation during Study 1:** As compensation for their time to bring the participant to the study, parent/legal guardian will receive \$10 in cash or gift card.
- **Participant compensation during Study 2:** Each study participant will receive compensation at different stages of the trial, proportional to the amount of participation (\$5 in cash or gift card for the baseline assessment, \$10 in cash or gift card for the mid-intervention assessment and 2 sessions, \$15 in cash or gift card for the post-intervention assessment and the remaining sessions, and \$20 in cash or gift card for the follow-up assessment and interview). Participants will receive \$5 in cash or gift card each time they complete Assessments 5 through 7, and \$10 in cash or gift card for completing assessment 8.
- **Parent compensation during Study 2:** As compensation for their time to bring the participant to the study, parent/legal guardian will receive \$20 in cash or gift card.

For Study 2, Appendix 19 presents a script of communication concerning compensation via e-mail, mail, or communication concerning compensation via phone.

- **Site compensation for Study 1 and Study 2:** Each participating ASP will receive a \$30 per participating adolescent as compensation for using regular club hours to allow their adolescents to participate and for facilitating the study. To avoid ASPs coercing adolescents into participating for compensation, each ASP will be blind to the number of participants from their program.
- **Program implementers compensation during Study 2:** For participating in a focus group discussion, each of the 10 program implementers will receive a \$20 compensation in cash or gift card after the focus group discussion.
- **After-school program staff compensation during Study 2:** For participating in an interview, each of the 10 ASP staff will receive a \$10 in cash or gift card.

- **School teacher compensation during Study 2:** Two school teachers implementing the program in their classes will receive a \$150 in cash or gift card for participating in the interview and implementing the program.
- The study team may request email address information from the Boys and Girls Clubs and PKY.

## 12. Conflict of Interest:

- The PI, co-I, or the University of Florida have no real conflicts of interest to this research project. The PI or the University of Florida currently have no intention in licensing or filing a patent application at a later date.

